### 12.8.1 Analysis of Unsolicited and Solicited AEs

An overall summary of unsolicited AEs will be prepared for AEs occurring within 28 days after each dose, within 28 days after any dose, and all reported AEs (including those reported at more than 28 days after any dose), presenting the number and percentage of subjects with

---

- Unsolicited AEs
- related unsolicited AEs
- grade 3 (severe) unsolicited AEs
- grade 3 (severe) related unsolicited AEs
- SAEs (includes solicited AEs)
- related SAEs (includes solicited AEs)
- intercurrent medical conditions affecting immune response (includes solicited AEs)
- AESIs (includes solicited AEs)
- related AESIs (includes solicited AEs)
- medically attended AEs (includes solicited AEs)
- related medically attended AEs (includes solicited AEs)
- AEs leading to vaccine withdrawal (includes solicited AEs)
- AEs leading to withdrawal from trial (includes solicited AEs)

The overall summary will also be presented by sex (female/male) for any dose regardless of retrospective serology status at baseline.

The following summaries of AEs by SOC and PT will further be provided, separately for AEs occurring within the first 28 days after each vaccination, within the 28 days after any vaccination, and all reported AEs (including those reported at more than 28 days after any dose) if not otherwise stated:

- Occurrence of unsolicited AEs
- Occurrence of related unsolicited AEs
- Occurrence of unsolicited AEs by maximum severity (mild / moderate / severe)
- Occurrence of related unsolicited AEs by maximum severity (mild / moderate / severe)
- Occurrence of SAEs (includes solicited AEs)
- Occurrence of related SAEs (includes solicited AEs)
- Occurrence of SAEs by maximum severity (mild / moderate / severe) (includes solicited AEs)
- Occurrence of related SAEs by maximum severity (mild / moderate / severe) (includes solicited AEs)
- Occurrence of intercurrent medical conditions affecting immune response (includes solicited AEs)
- Occurrence of AESIs (includes solicited AEs)
- Occurrence of related AESIs (includes solicited AEs)
- Occurrence of medically attended AEs (includes solicited AEs)
- Occurrence of related medically attended AEs (includes solicited AEs)
- Occurrence of AEs leading to vaccine withdrawal (includes solicited AEs)
- Occurrence of AEs leading to withdrawal from trial (includes solicited AEs)
- Occurrence of AEs related to SMQs as defined in Section 10.5.9 (includes solicited AEs)

A listing of all SAEs will further be provided by subject, including both unsolicited and solicited AEs.

---

Further AE listings supporting the AE tables described above will include both relevant solicited and unsolicited AEs. Solicited AEs occurring on the day of vaccination and the following 7 days and unsolicited AEs will be listed together.

## 12.8.2 Analysis Solicited AEs

The following summaries of solicited AEs within 7 days after each trial vaccination and within 7 days after any trial vaccination will be provided:

- Summary of solicited AEs, local AEs and systemic AEs, overall and by maximum grade
  - will also be presented by sex (female/male) for any dose, dose 1, dose 2 and booster dose regardless of retrospective serology status at baseline.
- Occurrence of local AEs, overall and by maximum grade
- Occurrence of systemic AEs, overall and by maximum grade
- Occurrence of related systemic AEs, overall and by maximum grade (mild / moderate / severe)
- Duration (days) of solicited AEs, overall and for grade 3 events
- Duration (days) of local AEs, overall and for grade 3 events
- Duration (days) of systemic AEs, overall and for grade 3 events
- Duration (days) of related systemic AEs, overall and for grade 3 events
- Daily summary of local AEs (only for each dose)
- Daily summary of systemic AEs (only for each dose)
- Daily summary of related systemic AEs (only for each dose)
- Summary of time of onset (Day) for grade 3 solicited AEs, any solicited AEs, local, systemic AEs, and related systemic AEs
- Time of onset (Day) of local AEs
- Time of onset (Day) of systemic AEs
- Time of onset (Day) of related systemic AEs
- Number and percentage of subjects with solicited Grade 3 adverse reaction(s) or SAEs considered as related to the trial vaccine according to the Investigator with the 95% credibility interval based on the Beta (0.5, 0.5) prior distribution for each dose level and dose will be calculated and summarized.
- Individual solicited local and systemic adverse events will be displayed in by-subject figures
- Individual grade 3 solicited local and systemic adverse events will be presented in a figure.

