9.1.6 Safety Monitoring Committees

If any SAE considered as related to the trial vaccine according to the Investigator occurs at any moment during the trial, all vaccinations will be put on hold. The DSMB will perform a comprehensive review of all relevant safety and reactogenicity data before making a decision to stop, continue, or modify vaccination (including evaluating lower doses).

The DSMB may recommend additional measures including modification or halt of the trial.

Group 2 (subjects >60 years, 6 µg) will be initiated in 4 sentinel subjects. These subjects should be vaccinated at least 60 minutes apart. Safety and reactogenicity data reported during an observation period of at least 24 hours after vaccination will be collected and reviewed by an iSRC. In this review, the iSRC will review all available safety data, but focus specifically on Grade 3 adverse reactions (defined as solicited systemic, solicited local, or unsolicited Grade 3 AEs considered as related to the trial vaccine). Based on this review, the iSRC will decide on continuation of enrollment of subjects at this dose level. In a next step, 8 additional sentinel subjects will be enrolled. Safety and reactogenicity data reported during an observation period of at least 24 hours after vaccination will be collected and reviewed by the iSRC. In this review, the iSRC will review all available safety data, but focus specifically on Grade 3 adverse reactions. The same procedure will be followed for Group 4 (subjects >60 years, 12 µg) and the iSRC will decide on continuation of enrollment of subjects at this dose level after review of the first 12 sentinel subjects.

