10.2 Populations for Analyses

Safety Set

The safety set will consist of all subjects who received at least 1 dose of trial vaccine and for whom any post-vaccination safety data are available.

Immunogenicity Set

The immunogenicity set will include all subjects who received at least 1 dose of trial vaccine and for whom the baseline blood sample and at least 1 additional blood sample are available for analysis.

In case a dose level has not been previously administered in Trial CV-NCOV-001, a dose-determining set (DDS) is defined and will consist of 4 additional subjects in the respective dose level and will be part of the safety set, who have either experienced Grade 3 adverse reactions or SAEs considered as related to the trial vaccine according to the Investigator at any time during the first 24 hours, or completed the 24-hour observation period without experiencing Grade 3 adverse reactions or SAEs considered as related to the trial vaccine according to the Investigator. The DDS will be used to confirm the safety on untested dose level prior to enrollment into the randomized part at the particular dose level. The minimum vaccination and safety evaluation requirements will have been met if the subject has received the planned dose of CVnCoV, has been observed for at least 24 hours following the first vaccine administration and has completed the required safety evaluation. Subjects who do not meet these requirements will be regarded as ineligible for inclusion in the DDS. Since DDS is only used to confirm safety prior to randomization, the DDS is not reported in the tables but Grade 3 adverse reactions and SAEs considered as related to the trial vaccine according to the Investigator used for the analyses are marked in the listings.

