10.3.5 Primary Analysis

10.3.5.1 Primary Safety Analysis

The safety measurements will include:

1. AEs (type, intensity, frequency and relationship to trial vaccination), i.e., incidence and severity of AEs for both solicited local (injection site pain, redness, swelling, and itching) and solicited systemic events (fever, headache, fatigue, chills, myalgia, arthralgia, nausea/vomiting, and diarrhea) occurring on the day of vaccination and the

following 7 days) and unsolicited events (occurring on the day of vaccination and the following 28 days).

2. SAEs and AESIs throughout the trial.

Solicited AEs: For reactogenicity assessment, for each dose level and dose in each phase, the number and percentage of subjects with at least 1 solicited AE of any kind, by severity grade, for local, systemic, and overall, will be summarized after the first vaccination, after the second vaccination, after the booster vaccination (if applicable), and after any vaccination. In addition, results from the expansion phase will be tabulated by group. For subjects with more than 1 episode of the same event, the maximum severity will be used for tabulations. In addition, for each dose level and dose in the dose escalation and expansion phases, the frequencies and severity of each solicited AE will be summarized for each vaccination day and the following 7 days. Similar tabulations will be performed for solicited systemic AEs considered as related to the trial vaccine. The duration and severity of solicited AEs will be analyzed at subject level.

In addition, other indicators of safety (e.g., body temperature) will be collected and summarized. The number and percentage of subjects with Grade 3 adverse reaction(s) or SAEs considered as related to the trial vaccine according to the Investigator with the 95% credibility interval based on the Beta (0.5,0.5) prior distribution for each dose level and dose will be calculated and summarized.

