### 6.1 Changes from Protocol

CMI response On Day 1, Day 29, and Day 43 in peripheral blood mononuclear cells (PBMCs) in a subset of subjects, will not be analyzed as part of this SAP, but listed only.

Evaluation of asymptomatic SARS-CoV-2 infection will be summarized by time point based on retrospective serology and RT-PCR results.

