#### 10.5.8 Adverse Reactions

Adverse reactions are defined as solicited systemic, solicited local and Grade 3 unsolicited (AEs) considered as related to the trial vaccine according to the investigator.

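### SAP 12.8.2 limits the Grade 3 composite to solicited reactions without declaring it, and the SAP does not confine the Beta(1.9, 0.1) seroconversion prior to CVnCoV groups

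*SAP*

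**What the plan says.** Protocol 10.3.5.1 plans, with a 95% credibility interval from a Beta(0.5, 0.5) prior and by dose level and dose: "The number and percentage of subjects with Grade 3 adverse reaction(s) or SAEs considered as related to the trial vaccine according to the Investigator". The sentence stands at the end of the block on solicited AEs and states no time window. The list that opens the same section covers solicited events for the vaccination day plus 7 days, "unsolicited events (occurring on the day of vaccination and the following 28 days", and SAEs throughout the trial.

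SAP 12.8.2 keeps the prior and almost the whole sentence, but begins it with "Number and percentage of subjects with solicited Grade 3 adverse reaction(s) or SAEs considered as related to the trial vaccine according to the Investigator". The bullet belongs to a list introduced by "The following summaries of solicited AEs within 7 days after each trial vaccination and within 7 days after any trial vaccination will be provided".

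The term itself is defined in three places:

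- Protocol 9.1.6, on the iSRC review of Grade 3 adverse reactions: "defined as solicited systemic, solicited local, or unsolicited Grade 3 AEs considered as related to the trial vaccine".
- SAP 11.2 repeats that definition.
- SAP 10.5.8, the derivation section: "Adverse reactions are defined as solicited systemic, solicited local and Grade 3 unsolicited (AEs) considered as related" to the trial vaccine in the investigator's view.

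SAP 6.1 lists two changes from the protocol: CMI data are listed only, and "Evaluation of asymptomatic SARS-CoV-2 infection will be summarized by time point based on retrospective serology and RT-PCR results".

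For seroconversion, SAP 9.4 and 12.9.1 give an estimate and credibility interval under Beta(1.9, 0.1), beside the exact Clopper-Pearson interval, for spike and neutralizing antibodies. Neither section names the arms to which the prior applies. SAP 12.0 presents CVnCoV, active control and total unless otherwise stated.

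**The concern.** One added word changes which subjects count in the only Grade 3 output that carries a credibility interval. A subject whose only Grade 3 reaction is a related unsolicited event is an adverse-reaction case under Protocol 9.1.6, SAP 11.2 and SAP 10.5.8, but not under SAP 12.8.2. The change runs one way: the count under the SAP wording is at most the count under the wider definition. Safety is a primary objective, and both documents give an acceptable rate of Grade 3 adverse reactions as a design aim.

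SAP 10.5.8 has a separate wording fault. It attaches Grade 3 only to unsolicited events, so a mild solicited event counts there as an adverse reaction alongside a severe unsolicited one.

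The secondary concern is about controls. A prior with mean 95% was chosen for vaccine response. In a small control group with few or no seroconverters it would dominate the estimate.

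**Working it through.** **Step 1. The event, side by side.**

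| Place | Related Grade 3 solicited | Related Grade 3 unsolicited | Window given |
|---|---|---|---|
| Protocol 10.3.5.1, composite sentence | yes | not excluded | none |
| Protocol 9.1.6 and SAP 11.2 | yes | yes | iSRC review of data from at least 24 hours |
| SAP 10.5.8 | yes, but at any grade | yes | none |
| SAP 12.8.2 | yes | no | 7-day lead-in |

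Solicited collection covers the vaccination day plus 7, or 8 days. Unsolicited collection covers the vaccination day plus 28, or 29 days. Deleting *solicited* while leaving the bullet under its present lead-in would still put 29 − 8 = 21 days of unsolicited follow-up in doubt.

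**Step 2. The formula.** SAP 10.5.10 gives the estimate as (x + α)/(n + α + β), with limits at the 2.5% and 97.5% quantiles of Beta(x + α, n − x + β). Check against Protocol Table 6: for 190 of 200 under Beta(1.9, 0.1), (190 + 1.9)/(200 + 2) = 95.0%, with limits 91.6 to 97.6. This agrees with the printed 95 (91.6–97.6).

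**Step 3. Size of the Grade 3 effect.** The documents give no Grade 3 counts, so all counts here are assumptions. SAP 12.0 presents the expansion cohort together with the initial phase, so at 12 µg each age group has 90 + 200 = 290 subjects. Take 58 subjects (20%) with a solicited case, and add a share who have only an unsolicited related Grade 3 event:

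| Added share | Cases of 290 | Estimate under Beta(0.5, 0.5) | 95% interval |
|---|---|---|---|
| 0% | 58 | 58.5/291 = 20.1% | 15.7–24.9 |
| 1% (2.9, taken as 3) | 61 | 61.5/291 = 21.1% | 16.6–26.0 |
| 2% (5.8, taken as 6) | 64 | 64.5/291 = 22.2% | 17.6–27.1 |
| 3% (8.7, taken as 9) | 67 | 67.5/291 = 23.2% | 18.5–28.2 |

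The estimate moves by about the omitted share. One subject weighs more in a booster subgroup of 30: 3/30 gives 11.3% (2.9–24.3) and 4/30 gives 14.5% (4.7–28.7).

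**Step 4. Controls under the seroconversion prior.** The prior mean is 1.9/(1.9 + 0.1) = 95%. Protocol Table 5 has 10 initial-phase controls per age group, and Table 2 adds 20 per age group in the expansion. Under Protocol Table 1, neutralizing activity is measured only in the initial phase, so each age group has 10 controls for neutralizing antibodies and 10 + 20 = 30 for spike antibodies. With assumed counts:

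| Seroconverters | Estimate under Beta(1.9, 0.1) | Credibility interval | Clopper-Pearson |
|---|---|---|---|
| 0/10 | 1.9/12 = 15.8% | 2.0–40.1 | 0–30.8 |
| 1/10 | 2.9/12 = 24.2% | 5.6–50.8 | 0.3–44.5 |
| 0/30 | 1.9/32 = 5.9% | 0.7–16.2 | 0–11.6 |
| 3/30 | 4.9/32 = 15.3% | 5.3–29.4 | 2.1–26.5 |

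With no seroconverters the credibility interval excludes the observed 0%, while the exact interval beside it starts at 0.

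**The case against.** The strongest reply is that the protocol sentence closes the solicited block, that the paragraph on unsolicited events plans no such rate, and that SAP 12.8.2 only makes the placement explicit. This stands in part: the restriction may be intended. A reader might infer that the protocol plainly requires the wider event over 28 days. It does not, because the sentence has no window and its position is ambiguous. What remains is that the SAP settled the ambiguity against its own derivation section without recording the choice in SAP 6.1.

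A reader might also lean on the dose-determining set (Protocol 10.2, SAP 9.5.3), which takes in subjects "who have either experienced Grade 3 adverse reactions or SAEs considered as related to the trial vaccine according to the Investigator". That text repeats the phrase without defining it, and the set is used only for dose levels not given before. It does not show that unsolicited events count.

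Nor are the omitted events lost. SAP 12.8.1 tabulates related Grade 3 unsolicited AEs and related SAEs after each dose and overall, and the SAP bullet does tell its reader that it is solicited. That answers any charge of concealment. It does not restore the combined rate: a subject may appear in both tables, so the rate and its interval cannot be rebuilt from them.

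Finally, the lead-in might be read as cutting off related SAEs after day 7. The bullet names SAEs separately and *solicited* qualifies only the reactions, so the text is unclear rather than exclusionary.

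On controls, Protocol 10.3.5.2 summarises by dose level and the humoral objective concerns CVnCoV, so use of the prior in controls may never have been meant. The SAP does not rule it out.

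**Conclusion.** The main point holds as an undeclared and internally inconsistent restriction. SAP 12.8.2 leaves related unsolicited Grade 3 events out of a composite for which SAP 10.5.8, SAP 11.2 and Protocol 9.1.6 include them. The reported rate can only stay equal or fall. On the assumed base of 58/290 the shortfall is 0 to about 3 percentage points for an omitted share of 0% to 3%, with overlapping intervals.

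A reader might infer that this could reverse a decision on acceptable reactogenicity. At an assumed 60/200 the posterior probability that the rate is at most 33% is 0.82, and at 62/200 it is 0.72, on either side of the 80% condition used for sizing. But no planned analysis decision uses that condition, and the trial is descriptive, so no error rate or conclusion rule is affected.

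The control-arm point rests on the SAP's display defaults, not on an explicit instruction. If those defaults are followed and no control seroconverts, the figures are 15.8% (2.0–40.1) at 0/10 and 5.9% (0.7–16.2) at 0/30. The exact interval beside them softens the effect but does not explain the contradiction.

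**What to change.** 1. In SAP 12.8.2, delete *solicited* and move the bullet out of the 7-day list. Count a subject with any related Grade 3 solicited AE (vaccination day plus 7), any related Grade 3 unsolicited AE (vaccination day plus 28) or any related SAE. Because the output is given per dose, assign each SAE to the most recent dose for the per-dose rows and show all SAEs in the any-dose row. Apply the SAP 10.8 censoring.
2. Reword SAP 10.5.8 to match Protocol 9.1.6, so that Grade 3 applies to solicited and unsolicited events alike.
3. If the restriction is intended, list it in SAP 6.1 and label the output as solicited only, in place of item 1.
4. In SAP 9.4 and 12.9.1, limit Beta(1.9, 0.1) to CVnCoV groups and report controls with the Clopper-Pearson interval already planned.

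The cost is SAP wording, one safety output specification and one clause on the prior. The reported Grade 3 rate may rise slightly. Data collection and the sizing tables do not change.

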## 12.9 Immunogenicity Analysis

### 12.9.1 Primary Immunogenicity Analyses

The primary immunogenicity will be analyzed for day 29 and 43. The primary humoral response endpoints will be analyzed with the immunogenicity set population for all available time points. All tables will be presented overall and by retrospective serology status (seropositive and seronegative) at baseline (see section 10.6.3). The primary immunogenicity endpoint will be analyzed with the immunogenicity set (see section 9.5.2). Once a subject (eligible for a booster dose) received the booster dose, the subject's measurement will be censored at the day after receiving the dose. Subjects receiving a booster dose will be analyzed separately.

The following two types of analyses will be performed:

- Estimate and 95%-credibility (using the prior beta(1.9, 0.1) intervals and proportion and 95%-confidence intervals (exact Clopper-Pearson) of subjects seroconverting with a 2-fold (definition for subjects seropositive at baseline) 4-fold increase, and any increase for subjects seronegative at baseline for SARS-CoV-2 spike (RBD) protein antibodies, as measured by ELISA, and serum SARS-CoV-2 neutralizing antibodies.

Geometric mean (GM), geometric standard deviation (GSD), 95%-confidence intervals and fold change of serum SARS-CoV-2 spike (RBD) protein antibodies, as measured by ELISA, and serum SARS-CoV-2 neutralizing antibodies.

Analysis for subjects eligible (and receiving) booster dose at day 57 or day 180 will be presented separately.

In addition, the following figures will be presented for serum SARS-CoV-2 spike (RBD) protein antibodies, as measured by ELISA, and serum SARS-CoV-2 neutralizing antibodies. All figures will be presented overall and by retrospective serology status (seropositive and seronegative) at baseline, except for subjects receiving a booster dose at day 57 or day 180 and are seropositive at baseline. For these no figures will be presented. All figures will be presented by overall age, age groups and dose level:

- Individual line plots.
- Line plots of fold change from baseline.
- Line plots of mean fold change from baseline (with 95% confidence intervals).
- Line plots of geometric mean titers (with 95% confidence intervals).
- Line plot of geometric mean fold change from baseline.

Box plot of geometric mean, minimum, Q1, median, Q3 and maximum. All immunogenicity data will be listed.

